5.2 Interim analysis

No Interim analyses are planned for this study. However, primary outcome data will be reviewed regularly by the independent data monitoring committee (IDMC) alongside safety data. The IDMC may recommend early trial cessation to the trial steering committee (TSC) based upon such data.

5.3 Analysis of primary outcome

The primary outcome (pleurodesis failure at 90 days post randomisation) will be analysed using a logistic regression model. As specified above, the model will adjust for the minimisation variables, and will exclude patients with missing outcome data.

5.4 Analysis of secondary outcomes

5.4.1 Pleurodesis failure at 30 days post randomisation

Data will be analysed in the same manner as the primary outcome, using a logistic regression model.

5.4.2 Pleurodesis failure at 180 days post randomisation

Data will be analysed in the same manner as the primary outcome and as for pleurodesis failure at 30 days post randomisation.

5.4.3 Percentage radiographic (chest x-ray) pleural opacification

The percentage chest x-ray pleural opacification will be analysed using a mixed-effects linear regression model, with a treatment-by-time interaction. Treatment effects will be presented for the discharge, 1-month, 3-month and 6-month follow-up visits.

The analysis will be performed in Stata as follows:

mixed outcome treat##time covariates || subject id:, noconstant residual(unstructured, t(time))

where *outcome* refers to the chest x-ray pleural opacification value, *treat* refers to the treatment variable, *time* refers to the study visit, and *covariates* refers to the covariates to be included in the analysis, which are the minimisation factors.

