1.3 Trial intervention

Patients will be randomised, in a 1:1 ratio using minimisation with a random element, to undergo either chest drain insertion with talc slurry pleurodesis or thoracoscopy with talc poudrage. Randomisation will be performed using a central telephone service and will take place following consent. The allocated trial intervention will take place within 72 hours of the allocation being determined.

Due to the inherent and substantial differences between the two methods being tested, this trial cannot be performed ethically or safely in a blinded manner using dummy or sham procedures. The trial will therefore be undertaken in an open-label manner, such that both the trial participant and the research team are aware of the allocated intervention.

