1.5 Changes from v1.0 of the Statistical Analysis Plan

- Changed method of analysis for pleurodesis failure from competing risk time-to-event model to logistic regression model (as was specified in the protocol)
- Removed secondary outcome 'Requirement for further pleural procedures up to 180 days post randomisation, based on an independent, blinded assessment'. This was because:
 - Blinded assessment and corroboration of the need for pleural intervention were already required for any case which is likely to be contentious, as per section 1.4 above.
 - Without clinical contact, the information upon which the assessment would be made was felt to be insufficient to determine whether a further pleural procedure would have been necessary, and thus the clinical relevance of the outcome was felt to be doubtful
 - It is likely that this assessment would rely primarily on the patient's x-ray appearance, which is being addressed as another secondary outcome.
- Restricted subgroup analyses to only the primary outcome
- Updated Stata command for analysing chest x-ray pleural opacification, EQ-5D, SF36, thoracic pain, and breathlessness, from *xtmixed* to *mixed* (the command *mixed* replaced *xtmixed* in more recent versions of Stata)

- Removed sensitivity analysis for primary outcome based on measure pleurodesis failure from date of procedure rather than date of randomisation.
- Removed the subgroup analysis for use of NSAIDs at baseline as this question has now been addressed in the TIME1 trial
- Removed the subgroup analysis for previous radiotherapy at baseline
- Added additional exploratory outcomes
- Specified that adverse events and serious adverse events would be summarised and analysed within 7 days of randomisation (in addition to within 30 and 180 days)

All changes to the Statistical Analysis Plan were made before database lock.

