3. SAMPLE SIZE

Previous literature and our own audit data suggest that patients with a WHO performance status score of 2 or better have approximate pleurodesis failure rates of 10% with a thoracoscopy, and 30% with standard chest tube and talc slurry pleurodesis.[5]

In order to detect a 15% difference in pleurodesis failure at 3 months (10% thoracoscopy and poudrage vs. 25% chest drain and talc slurry) with 90% power, a 5% significance level, and 10% loss to follow-up, we would require 325 patients. This has been rounded up to 330 patients (165 patients in each treatment arm).

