5. ANALYSIS PRINCIPLES

5.1 General principles for analysis

The primary analysis for each outcome will be by intention-to-treat, meaning that all patients on whom an outcome is available will be included in the analysis, and will be analysed according to the treatment group to which they were randomised. More information on which patients are considered to have an available outcome is available in later sections. All tests will be two-sided, and will be considered statistically significant at the 5% level.

For each analysis, the following summaries will be provided:

- The number of patients in each treatment group who are included in the analysis
- The mean (SD) or median (IQR) in each treatment group for continuous outcomes, or the number (%) of patients experiencing an event for binary or time-to-event outcomes (time-to-event outcomes will also present the median time to event in each treatment arm if applicable)
- The treatment effect (difference in means for continuous outcomes, odds ratio for binary outcomes, hazard ratio for time-to-event outcomes, rate ratio for count outcomes) with its 95% confidence interval and a p-value

All analyses will adjust for the minimisation variables (type of underlying malignant disease [mesothelioma, lung cancer, breast cancer, other] and WHO performance status [0-1 or 2-3]).[6-8] Minimisation variables will be included as covariates in the regression model for each outcome.

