5.4.4 EQ-5D

Self-reported quality of life using the EQ-5D questionnaire will be analysed using a mixed-effects linear regression model, with a treatment-by-time interaction. In addition to the minimisation factors, the analysis will also adjust for baseline EQ-5D. Missing values of baseline EQ-5D will be imputed using mean imputation [9]. Treatment effects will be presented for the 1-month, 3-month and 6-month follow-up visits. The Stata code used for analysis is the same as for pleural opacification above.

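### The printed mixed-model command names neither REML nor a degrees-of-freedom method, so 6-month intervals for five secondary outcomes come out slightly too narrow

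*SAP*

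**What the plan says.** Section 5.4.3 specifies a linear mixed model with a treatment-by-time interaction for opacification and prints the Stata line to be used: "mixed outcome treat##time covariates || subject id:, noconstant residual(unstructured, t(time". The text after it explains what the outcome, treatment, time and covariate names stand for. It does not mention an estimation method or a reference distribution.

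Section 5.4.4 (EQ-5D) says "The Stata code used for analysis is the same as for pleural opacification above", and section 5.4.6 (thoracic pain) says the same. SF-36 follows EQ-5D, and breathlessness follows thoracic pain. One line therefore governs five secondary outcomes.

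The covariates are the minimisation factors, "type of underlying malignant disease [mesothelioma, lung cancer, breast cancer, other] and WHO performance status [0-1 or 2-3", plus the baseline value for all of these outcomes except opacification. Section 5.1 sets the inferential standard: "All tests will be two-sided, and will be considered statistically significant at the 5% level", with 95% confidence intervals for every treatment effect.

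Section 1.5 records that the command name was updated because "the command *mixed* replaced *xtmixed* in more recent versions of Stata". It gives no version number and does not mention estimation.

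**The concern.** When a SAP prints the command, the options left out of it matter as well as those put in. Without `reml`, `mixed` uses maximum likelihood, which makes no allowance for the estimated fixed effects and so understates the residual variances. Without a degrees-of-freedom option it refers the estimate to the normal distribution, as if those variances were known. Both errors narrow the interval.

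Under an unstructured covariance, the variance at each visit is learned mainly from the patients measured at that visit. The effect is therefore largest at 6 months, after deaths and losses. For opacification, section 2.2.2 also stops readings at the first fluid intervention on the trial side.

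What is at stake is whether the 6-month intervals and p-values for these secondary outcomes hold the 95% and 5% levels that section 5.1 promises.

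**Working it through.** **1. The plan's own figure.** The only sample size in the SAP is for the primary outcome. Section 3 assumes failure rates of 10% with poudrage and 25% with slurry, and concludes: "with 90% power, a 5% significance level, and 10% loss to follow-up, we would require 325 patients". With mean proportion 0.175:

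- Uncorrected: [1.96·√(2·0.175·0.825) + 1.2816·√(0.1875 + 0.09)]² / 0.15² = 1.7283² / 0.0225 = 132.8, so 133 per arm.
- Continuity-corrected: (132.8/4)·[1 + √(1 + 4/(132.8·0.15))]² = 145.8, so 146 per arm and 292 in total.
- With 10% loss: 292/0.9 = 324.4, so 325.

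The stated 325 reproduces. It says nothing about the continuous outcomes, for which the SAP gives no standard deviation or precision target.

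**2. Fixed effects in the printed model.** Terms are intercept + treatment + time + interaction + minimisation dummies (3 + 1) + baseline.

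- EQ-5D and SF-36 (three visits): 1 + 1 + 2 + 2 + 4 + 1 = 11
- Opacification (four visits, no baseline term): 1 + 1 + 3 + 3 + 4 = 12
- Pain and breathlessness (four visits): 1 + 1 + 3 + 3 + 4 + 1 = 13

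**3. Patients with 6-month data (assumption).** The SAP gives no number. As a working range, take exponential survival from randomisation with a median of 4 to 6 months, borrowing the range in section 1.1.

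- Alive at 6 months: 330 × 0.354 = 117 to 330 × 0.50 = 165
- After 10% loss: about 105 to 148
- For x-rays, removing a further 17.5% (mean of the planned 10% and 25% failure rates): about 87 to 122

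This gives a range of roughly 85 to 150. The check below also goes down to 40.

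**4. Single-visit approximation.** With p = 6 (intercept, treatment, four dummies), the width of a maximum likelihood z interval relative to a REML t interval is √((n − p)/n) × 1.96 / t(0.975; n − p).

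| n | width ratio | coverage, ML with z |
|---|---|---|
| 330 | 0.9909 × 1.9600/1.9673 = 0.987 | 94.7% |
| 150 | 0.9798 × 1.9600/1.9766 = 0.972 | 94.3% |
| 100 | 0.9695 × 1.9600/1.9855 = 0.957 | 94.0% |
| 60 | 0.9487 × 1.9600/2.0049 = 0.927 | 93.2% |
| 40 | 0.9220 × 1.9600/2.0322 = 0.889 | 92.0% |

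This treats each visit alone and overstates the narrowing, because the joint model also uses earlier visits. The n = 330 row shows how little there is to correct while nearly everyone is still measured.

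**5. Simulation of the printed model.** Settings: 330 patients, four visits, unstructured covariance, 13 fixed effects, monotone dropout. Assumed visit SDs were 20-26 and correlations 0.4-0.6. There were 2,000 runs for n = 148 and 99, and 1,500 for n = 59 and 40. REML t used n − 7 degrees of freedom as a stand-in for a formal small-sample method. Results are for the 6-month treatment effect.

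| n at 6 months | SE ratio ML/REML | width ratio | coverage, ML with z | coverage, REML with t |
|---|---|---|---|---|
| 148 | 0.992 | 0.983 | 94.4% | 94.7% |
| 99 | 0.989 | 0.976 | 94.0% | 94.5% |
| 59 | 0.983 | 0.961 | 93.7% | 94.8% |
| 40 | 0.976 | 0.940 | 91.7% | 93.3% |

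The Monte Carlo standard error of each coverage is about 0.5-0.7 points, so the coverage differences at n = 148 and 99 are within or near that noise. The width ratios fall steadily as n falls. Dividing width ratio by SE ratio isolates the z-for-t part: 0.983/0.992 = 0.991 at n = 148 and 0.976/0.989 = 0.987 at n = 99. Each source contributes about half of the narrowing.

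**6. A second simulation.** This used exponential survival, 10-15% other missingness and 450 replicates per scenario, leaving about 77 to 149 patients at 6 months. SE ratios were 0.986-0.989. Combined with z in place of t on 70, 100 and 140 df, the width ratios are 0.969, 0.974 and 0.980. The analytic two-sided error rates 2·P(t > 1.96 × SE ratio) are 5.7%, 5.6% and 5.5%. Both simulations point to intervals about 2-3% too narrow.

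**The case against.** The strongest objection is that the effect is negligible. A width ratio of 0.969 to 0.980 means that a printed |z| of 1.96/0.980 = 2.00 to 1.96/0.969 = 2.02 is already enough for the REML-based test to reject as well. Only a 6-month result with a printed p-value between about 0.043-0.046 and 0.05 could change sides. Large-sample inference with 80 to 150 patients is ordinary practice. This stands, and it is why the point is minor.

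A second objection is that the defect depends on software defaults that the SAP never states, and that the printed line is a template with placeholders, not a considered choice of estimator. The first part is true and should be said openly. It does not remove the point: the SAP says the analysis will be run with this line, and nothing elsewhere supplies an estimator. At the least, estimator and reference distribution are left to the software.

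Three stronger readings are tempting, and the document does not support them:

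- **That few patients remain at 6 months, so the intervals are seriously wrong.** The SAP gives no 6-month number, and its figures suggest roughly 85 to 150.
- **That half or more will have died by then.** The survival figure in section 1.1 runs from diagnosis and describes malignant effusion in general. Follow-up here runs from randomisation, and section 1.2.1 admits only patients expected to survive more than 3 months.
- **That testing each visit at the 5% level makes this worse.** That is a multiplicity question, and changing the estimator would not address it.

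**Conclusion.** The point holds as a small, one-directional error in the 6-month results of five secondary outcomes. With about 85 to 150 patients at 6 months, the intervals are about 2-3% too narrow and cover about 94-94.5% instead of 95%. A changed conclusion is unlikely in that range. A material shortfall needs about 40-60 or fewer patients; at 40, coverage in the simulation fell to 91.7%, and the simple REML t interval itself reached only 93.3%. Early visits are essentially unaffected, and the primary logistic model in section 5.3 does not use this command.

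The size rests on the assumed 6-month numbers and on the assumed SDs and correlations. The mechanism rests on the known default behaviour of `mixed`, which the team can confirm from the output header of a single run.

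**What to change.** Add `reml` to the command in section 5.4.3, which carries it into sections 5.4.4 to 5.4.7. State that tests and intervals use a Kenward-Roger or Satterthwaite method. Confirm that the Stata version to be used supports the chosen method with an unstructured residual covariance, state that version, and name a fallback. Adding `reml` alone would remove only about half of the narrowing.

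The cost is one or two options on one line. Intervals at 6 months become about 2-3% wider and early-visit results barely move.

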5.4.4 EQ-5D

Self-reported quality of life using the EQ-5D questionnaire will be analysed using a mixed-effects linear regression model, with a treatment-by-time interaction. In addition to the minimisation factors, the analysis will also adjust for baseline EQ-5D. Missing values of baseline EQ-5D will be imputed using mean imputation [9]. Treatment effects will be presented for the 1-month, 3-month and 6-month follow-up visits. The Stata code used for analysis is the same as for pleural opacification above.

5.4.5 SF-36

The SF-36 health questionnaire will be analysed in the same manner as the EQ-5D.

5.4.6 Thoracic pain

Self-reported VAS scores for thoracic pain will be analysed using a mixed-effects linear regression model, with a treatment-by-time interaction. The analysis will adjust for the baseline value of thoracic pain (in addition to the minimisation factors, as mentioned in section 5.1). Missing baseline values of thoracic pain will be imputed using mean imputation. Treatment effects will be presented for the 1-month, 3-month and 6-month follow-up visits, and for the 7 days post randomisation. The Stata code used for analysis is the same as for pleural opacification above.

5.4.7 Breathlessness

Self-reported VAS scores for breathlessness will be analysed using the same methods as for thoracic pain.

5.4.8 Mortality

All-cause mortality up to 180 days post randomisation will be analysed using a logistic regression model.

5.4.9 Time to pleurodesis failure from randomisation

Time to pleurodesis failure will be analysed using a competing risk time-to-event regression model, with mortality as the competing risk. Patients who do not experience either the primary outcome or mortality will be censored at the point of last contact.

5.4.10 Number of days spent as a hospital inpatient up to 90 days post randomisation

The number of days spent as an inpatient from randomisation up to 90 days post randomisation will be analysed using a negative binomial regression model. The number of days of follow-up will be included in the model as an offset (i.e. the model will include a term for the log-transformed number of days of follow-up for each patient, with the parameter constrained to one).

5.4.11 Adverse events

Adverse events will be analysed using a logistic regression model. Analyses will be performed for adverse events up to 7, 30, and 180 days post-randomisation.

5.4.12 Serious adverse events

Serious adverse events will be analysed using a logistic regression model. Analyses will be performed for serious adverse events up to 7, 30, and 180 days post-randomisation.

5.4.13 Exploratory outcomes

The exploratory outcome of the categorical version of percentage radiographic pleural opacification will be analysed using a mixed-effects ordinal logistic regression model, with a random-intercept for patient. The model will be adjusted for the minimisation variables.

The exploratory outcome of the degree of visible lung entrapment will be analysed using an ordinal logistic regression model, adjusted for the minimisation variables.

5.5 Subgroup analyses

Subgroup analyses will be performed for the primary outcome. An interaction test will be used (i.e. an interaction term between the treatment and the baseline covariate will be added to the regression model), and will be considered statistically significant at the 5% level. Results from subgroup analyses will be viewed as hypothesis generating, and will not be used to make definitive statements about treatment efficacy in a specific subgroup of patients. The following subgroup analyses will be performed:

- Patients receiving anti-cancer therapy at baseline vs those not receiving anti-cancer therapy at baseline
- WHO performance status 0 vs 1 vs 2 vs 3
- Patients on steroids at baseline vs those not on steroids at baseline
- Previous attempt at pleurodesis within the last month vs. no attempt in the last month.
- Patients with primary malignancy of breast cancer vs. mesothelioma vs. lung cancer vs. other

5.6 Missing data

5.6.1 General comments

The primary outcome will be considered missing if there is no data regarding pleurodesis failure during the first 90 days post-randomisation. Secondary outcomes measuring pleurodesis failure will also be regarded as missing if there is no data available up to the specific time point.

EQ-5D, SF-36, and VAS for thoracic pain and breathlessness will be considered missing if no postrandomisation measurements are recorded.

Number of days in hospital, adverse events, and serious adverse events will be considered missing if the patient attends no follow-up visits, and outcome records are not available.

Chest x-ray opacification will be considered missing if there are no available x-ray data for analysis.

All-cause mortality will be considered missing if we are unable to obtain information on whether the patient was alive at the end of follow-up.

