2. OUTCOME MEASURES

2.1 Primary outcome measure

2.1.1 Primary outcome measure description

The primary endpoint is the number of patients who experience pleurodesis failure up to three months (90 days) post randomisation. The overall survival rate from diagnosis of malignant pleural effusion is generally only a few months. For this reason, the primary endpoint being measured at three months is likely to be a more clinically relevant period over which pleurodesis failure will impact on patient care and quality of life. The proportion of patients experiencing pleurodesis failure by 1 and 6 months (30 days and 180 days) will be secondary outcomes.

A patient is defined as experiencing pleurodesis failure if they undergo any of the following procedures on the side ipsilateral to their trial intervention:

- Therapeutic pleural aspiration of ≥100mls, or
- Insertion of an intercostal drain for fluid drainage, or
- Insertion of an indwelling pleural catheter, or
- Medical or surgical thoracoscopy

A patient is also deemed to have failed pleurodesis if their primary physician decides that they require one of the above pleural interventions, but the intervention is not performed (e.g. in the event of death or patient choice against procedure). A patient who does not meet the criteria for a pleurodesis failure will be deemed as having had a successful pleurodesis.

The primary physician is not blind to treatment arm, however all decisions to intervene or not in effusions which occupy less than or equal to one third of the hemithorax should be discussed with a second clinician who is to remain blind to treatment allocation.

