5.7 Sensitivity analyses

5.7.1 Missing data

Sensitivity to missing data for the primary outcome will be assessed under a range of missing-not-atrandom scenarios. This will be performed using the following formula:

$$\Delta = \Delta_{\rm CC} + Y_1 P_1 - Y_2 P_2$$

where Δ is the treatment effect under the missing-not-at-random scenario, Δ_{CC} is the treatment effect under a complete case scenario (i.e. where patients with a missing outcome are excluded), P₁ and P₂ are the proportion of patients who were excluded in groups 1 and 2 respectively, and Y₁ and Y₂ are the proportion of patients in treatment group 1 and 2 with missing data who are assumed to experience an event (i.e. who experience the primary outcome). For this sensitivity analysis, we will consider all patients who were excluded from the primary analysis due to missing data. We assume that the standard error for Δ is approximately equal to the standard error for Δ_{CC} .

 Y_2 will be varied between 10%, 25%, 50%, 75%, and 90% and for each value of Y_2 , Y_1 will be varied between Y_2 -10%, Y_2 , and Y_2 +10%. For example, for Y_2 =25%, Y_1 will vary between 15%, 25%, and 35%.

For each scenario, a treatment effect and 95% confidence interval will be calculated, which will be compared with results from the main analysis of the primary outcome to see if conclusions are affected by different assumptions regarding the missing data.

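### A patient with a failure-free follow-up record who is then lost alive before day 90 is analysed as a pleurodesis success, and the missing-data sensitivity analysis does not vary that assumption

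*SAP*

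**What the plan says.** Four parts of the SAP together fix the value of the primary outcome for a partly followed patient.

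- **Section 5.6.1** defines missing: "The primary outcome will be considered missing if there is no data regarding pleurodesis failure during the first 90 days post-randomisation". For days 30 and 180 it adds: "Secondary outcomes measuring pleurodesis failure will also be regarded as missing if there is no data available up to the specific time point".
- **Section 2.1.1** sets the default: "A patient who does not meet the criteria for a pleurodesis failure will be deemed as having had a successful pleurodesis". No minimum length of observation is attached.
- **Section 5.3** fits a logistic model that "will exclude patients with missing outcome data".
- **Section 5.7.1** limits the sensitivity analysis: "For this sensitivity analysis, we will consider all patients who were excluded from the primary analysis due to missing data".

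The secondary time-to-failure analysis in section 5.4.9 treats incomplete follow-up differently: "Patients who do not experience either the primary outcome or mortality will be censored at the point of last contact".

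The table in section 4.1 assigns data on pleurodesis failure to the follow-up form at months 1, 3 and 6. The visit windows in section 5.6.2 apply only to quality of life and symptom scores, so they set no follow-up requirement for the failure outcome.

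**The concern.** Take a patient who attends the month-1 visit without failure and is then lost alive. There are failure data within the first 90 days, so the outcome is not missing. No failure has been recorded, so the patient is a success. The plan thus fills in the favourable value for about two unobserved months in the primary analysis and, on the plain reading, about five in the day-180 analysis. In the SAP's Table 3 the same patient would be a success in the day-90 row and censored in the time-to-failure row.

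This pulls observed failure rates down in both arms. If loss is similar in the two arms, the comparison is barely affected. If loss differs, the comparison is biased in a direction that depends on which arm loses more. The trial is open-label and section 1.4 acknowledges the greater potential for bias, so differential loss cannot be ruled out in advance. The planned sensitivity analysis would not reveal the problem, because the definition of missing keeps these patients out of it.

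**Working it through.** **Inputs.** From SAP section 3: failure 10% (poudrage) and 25% (slurry), 90% power, 5% significance, 10% loss, 325 patients rounded up to 330 (165 per arm). From section 5.1: two-sided tests. The loss in each arm (L) and the share of lost patients' failures captured before loss (f) are not in the document. They are assumptions here.

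**The plan's own figure.** The two-proportion formula gives 133 per arm, or 146 with continuity correction. Then 2 × 146 = 292, and 292/0.9 = 324.4, which rounds up to 325. The stated figure reproduces. It treats lost patients as contributing no outcome, whereas section 5.6.1 keeps the partly followed ones as successes.

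**Observed rate under the rule.** q = p × (1 − L × (1 − f)). Power at n = 165 per arm, without continuity correction, is Φ of
(|q₂ − q₁| − 1.96 × √(2q̄(1 − q̄)/n)) / √((q₁(1 − q₁) + q₂(1 − q₂))/n).

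**Scenarios with a true effect, f = 0, every lost patient partly followed:**

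| Loss, poudrage / slurry | Observed rates | Difference | OR | Power under the rule | Power if excluded |
|---|---|---|---|---|---|
| 10% / 10% | 9.0% / 22.5% | 13.5 points | 0.341 | 92.4% | 92.9% |
| 5% / 15% | 9.5% / 21.25% | 11.75 points | 0.389 | 84.4% | 92.9% |
| 15% / 5% | 8.5% / 23.75% | 15.25 points | 0.298 | 96.8% | 92.8% |

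The true values are 15 points and OR 0.333. The last column uses the numbers left after exclusion (148.5 per arm with equal loss; 156.75 and 140.25 with unequal loss) and assumes that loss is unrelated to outcome.

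Second row in full:
- q₁ = 0.10 × 0.95 = 0.095; q₂ = 0.25 × 0.85 = 0.2125; q̄ = 0.15375.
- (0.1175 − 1.96 × 0.0397)/0.0392 = 1.01, and Φ(1.01) = 0.844.

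With f = 0.5 the 5%/15% case softens to 13.4 points, OR 0.359 and 91% power.

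**No true effect, 25% in both arms, 5%/15% loss, f = 0.**
- Observed rates: 0.25 × 0.95 = 23.75% and 0.25 × 0.85 = 21.25%. This is a spurious 2.5 points, OR 1.15.
- The standard error is 0.0460, so the shift is 0.025/0.0460 = 0.54 standard errors.
- Type I error is about 0.0061 + 0.0783 = 8.4%.
- With f = 0.5 the shift is 1.25 points and type I error about 5.8%.

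**What section 5.7.1 would see.** Ten per cent of 330 is 33 patients. If 90% of them had one earlier failure-free record (an assumption), 33 × 0.1 ≈ 3 enter the sensitivity analysis and about 30 remain as untested successes.

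**Why simply dropping them is not clean.** Take 10% loss and f = 0.5, keeping captured failures and dropping the failure-free losses. The observed rates become (0.09 + 0.005)/(0.90 + 0.005) = 10.5% and (0.225 + 0.0125)/(0.90 + 0.0125) = 26.0%, slightly above the true 10% and 25%.

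**The case against.** The strongest reply is that the harm is small unless loss differs by arm, and nothing in the document says that it will. This stands. The plan's effect measure is the odds ratio, which moves only from 0.333 to 0.341 under equal 10% loss, and power is within half a point of that under exclusion. A comparison with the 95% power at 165 per arm without any loss would overstate the damage, because part of that gap is ordinary loss to follow-up. The scenarios are also harsh in assuming that no failure is captured before loss.

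Three stronger readings are tempting, and the document does not carry them.

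- A reader might infer that any early contact, even a discharge form, turns a lost patient into a success. Section 4.1 places failure data on the follow-up form, while the discharge form covers the inpatient period and complications. The SAP does not say whether a discharge form alone would count. A patient lost on day 10 may well be missing, hence excluded and covered by 5.7.1. The month-1 case needs no such assumption.
- A reader might take the day-180 success as certain. The sentence on days 30 and 180 could also mean data reaching that time point. The plain reading matches the day-90 rule, but the wording is ambiguous.
- A reader might say that nothing in the plan could expose the problem. The competing-risk analysis in 5.4.9 censors these patients and appears in the same results table, so it gives an indirect check. It is a secondary outcome with a different estimand, and it is not designated as a sensitivity analysis for the day-90 result.

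**Conclusion.** The point holds for patients with a failure-free follow-up record who are lost alive before day 90. Sections 5.6.1, 2.1.1 and 5.3 make them successes by a stated rule, and 5.7.1 leaves them out.

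The effect is negligible under equal loss. It becomes material only under an assumed imbalance: at 5%/15% the difference falls to 11.75 points, power to 84%, and type I error under no effect rises to about 8.4%. The reverse imbalance slightly exaggerates the benefit (15.25 points, OR 0.298), so the direction cannot be predicted. All of these figures assume that every lost patient is partly followed and, except where f = 0.5 is stated, that none of their failures is captured. The document gives neither loss by arm nor timing of loss.

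This should be fixed, because the rule sets the value of the primary endpoint and is cheap to correct. The document does not support calling the primary analysis invalid.

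**What to change.** 1. In section 5.6.1, state that a patient who is alive, failure-free and last contacted before the time point has an unknown outcome at that time point, for days 30, 90 and 180 alike. Give a tolerance for how near the last contact must be, since a month-3 visit can fall shortly before day 90. Deaths stay as section 2.1.1 treats them.
2. State whether a discharge form alone counts as data on pleurodesis failure, and reword the day-30/180 sentence so that it has one meaning.
3. In the main logistic model, handle the unknown outcomes by multiple imputation using arm, minimisation factors and time of last contact, or by inverse-probability-of-censoring weights. Do not simply drop these patients while keeping captured failures.
4. Extend the missing-not-at-random analysis to them in one of two ways: vary the imputation assumption, or start from the complete-case estimate that excludes them and count them in P₁ and P₂. Section 5.7.1 defines P₁ and P₂ as proportions excluded, so doing both would adjust for the same patients twice.
5. Report the number of such patients by arm.

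The cost is SAP wording, modest analysis work and slightly lower precision. Last-contact dates are already needed for 5.4.9. The sample size does not change.
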